4.4. Serious and unexpected adverse events

There may be mortality and morbidity associated with either procedure, therefore all serious adverse events (SAE) should be reported by fax to the NOTABLE Trial Office as soon as possible. This report should be followed within 2 days by a completed SAE form to the Ethics Committee and the Federal Agency for Medicines and Health Products (FAMHP). For the purposes of this study, "serious" adverse events are those which are fatal, life-threatening, disabling or prolong hospitalisation and have resulted from the surgical procedure, the anaesthetic or post-operative recovery e.g. deep vein thrombosis, hospital acquired infections.

5. FOLLOW-UP AND OUTCOME MEASURES

5.1. Clinical assessments

5.1.1 Format

PROMs will be collected using a postal questionnaire at baseline, at three and six months.

The postal questionnaires will be sent from the NOTABLE Trial Office with postage paid envelopes two weeks before the due date. Reminders will be sent to the participants if the questionnaire is not returned within one week of the due date and attempts will be made to contact the women by phone if the questionnaire is not returned by two weeks after the due date.

5.1.2 Timing of assessments

The primary outcome will be measured clinically at the end of the surgical procedure. In addition PROMs will take place the evening of the surgical intervention (return home), during the first postoperative week (pain by VAS scores and medication) and at 3 and 6 months (dyspareunia and sexual wellbeing). Clinical physician assessment will take place the evening of the surgical intervention (return home) and during the first six weeks following surgery (pelvic infection, surgical complications).

5.2. Primary clinical outcome measure

The proportion of women successfully treated by removing the adnexal mass without spill, using a dichotomous outcome measure, will be used as a measure of efficacy. An important consideration in adnexal mass surgery is the inadvertent opening of the ovarian capsule. The likelihood of cyst rupture during removal by laparotomy or laparoscopy ranges from 10.5% to 41.8% in published studies (15). We will consider any spontaneous rupture of the cyst or any need to aspirate the cyst to allow removal from the abdominal cavity as treatment failures, even if the content of the ruptured cyst does not spill freely inside the cavity but remains within the endobag. By avoiding any subjective interpretations this rigorous definition allows an objective measure of success. As the risk of rupture may be associated to the cyst size, due to the stratified random sequence generation we anticipate that the risk of rupture due to the cyst size rather than the technique used will be symmetrically applicable.

5.3. Secondary clinical outcome measures

We will measure the following secondary outcomes:

- The proportion of women discharged the same day based on their own preference, as a dichotomous outcome. The decision to discharge from the day care unit or to admit to hospital for the night will be based solely on the choice of the woman to return home the same day or stay overnight. The outcome assessor will report this decision in the patient record without consulting the results of the pain scoring or whether or not additional

analgesics were administered. In case of conflict (women wishing to return home against outcome assessor's advice based on clinical suspicion of possible complications for instance) the study participant is not excluded from further follow-up. Data will be analysed using a sensitivity analysis by imputing that the index participant would have agreed to stay overnight as dictated by the clinical judgement of the outcome assessor versus the available data analysis.

- Postoperative pain scores, as an ordinal outcome, measured using a VAS scale twice daily from day 1 till 7 self-reported by the participating women: one measurement will be done in the morning after bed rest at night (rest) and the other will be done in the evening before going to bed after physical activity (active). The participants should place the cursor of the VAS scale device available at the day care unit of the participating centre on the picture indicating the expression of pain sensation that according to their own experience best describes how they feel pain at the time point of measurement. By looking at the back of the scale they can measure the level of pain by recording the numbers immediately to the left and right of the red line: e.g. pain level 0 to 1, or pain level 5 to 6. The lowest number will be recorded by the outcome assessor for data analysis. The reliability of VAS has been established in the assessment of chronic gynaecological conditions like pain.
- Postoperative pain defined by the total use of analgesics during the first week following surgery as described in the standardized pain treatment protocol, as an ordinal outcome. The use of pain medication following surgery should be reported in the nursing file. At home the participants should note in their participant log book the name, dosage, route of administration of any analgesic drug that was taken from the moment they are at home until the assessment on day 7 irrespective of whether this was done on their own initiative or after consulting a family physician or any other medical specialist. The assessment of the total use of analgesics will be done on day 7 by the outcome assessor (the coordinating investigator), who is blinded for the intervention done by the principal investigator.
- Postoperative infection defined by lower abdominal pain with fever $> 38^{\circ}\text{C}$ and positive clinical signs or laboratory findings, detected during the first six weeks of surgery, as a dichotomous outcome.
- Per- or postoperative complications according to the Clavien- Dindo classification detected during the first six weeks of surgery, as a dichotomous outcome (Appendix III).
- Hospital readmission during the first six weeks of surgery, as a dichotomous outcome.
- Incidence and intensity of dyspareunia recorded by the participants at 3 and 6 months by self-reporting using a simple questionnaire and VAS scale, as a dichotomous and ordinal

outcome. A measurement of the prevalence and the intensity of dyspareunia will be done at baseline assessment.

- Sexual wellbeing at baseline, at 3 and 6 months by self-reporting the SSFS.
- Quality of life at baseline, at 3 and 6 months by self-reporting the EQ-5D-3L questionnaire.
- Duration of surgery measured as the time in minutes from the insertion of the bladder catheter to the end of vaginal/abdominal wound closure, as a continuous outcome.

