Secondary outcomes: the proportion of women discharged the same day based on their own preference; postoperative pain scores using a VAS scale measured between day 1 till 7 by the participating women following surgery and the total use of analgesics as described in the standardized pain treatment protocol; postoperative infection defined by lower abdominal pain with fever $> 38^{\circ}\text{C}$ and positive clinical signs or laboratory findings; per- or postoperative complications according to the Clavien- Dindo classification (8) detected during the first six weeks of surgery; hospital readmission during the first six weeks of surgery; duration of the surgical procedure; incidence and intensity of dyspareunia recorded by the participants at 3 and 6 months by self-reporting using a simple questionnaire and VAS scale; sexual wellbeing recorded by the participants at 3 and 6 months by SSFS; quality of life by self-reporting the EQ-5D-3L questionnaire at 3 and 6 months; direct costs associated with both procedures.

Nature and extent of the burden and risks associated with participation, benefit and group relatedness: The burden and risks associated with the participation in the study are comparable with the risks related to the established technique of laparoscopic adnexectomy.

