We retrieved one RCT from Italy (16). Women scheduled for a laparoscopic resection of an adnexal mass were randomised to have their surgical specimen removed either through a posterior colpotomy (n = 34) or the umbilical port site (n = 32). Group allocation was concealed from study participants and bedside clinicians. The primary outcome was postoperative incisional pain assessed by a 10-cm visual analogue scale at 1, 3, and 24 hours after surgery. Transvaginal retrieval caused less postoperative pain than transumbilical specimen extraction at each time point (visual analogue scale score at 1 hour: 2.6 ± 2.9 vs 1.2 ± 2.0 , $P = 0.03$; at 3 hours: 2.4 ± 2.0 vs 1.4 ± 2.0 , $P = 0.02$; and at 24 hours: 1.1 ± 1.5 vs 0.5 ± 1.4 , $P = 0.02$). A higher proportion of women in the transumbilical group than in the transvaginal group indicated the umbilicus as the most painful area at 1 and 3 hours postoperatively. Two months after surgery, the participants scored similarly as to their overall satisfaction, cosmetic outcome, and dyspareunia upon resumption of intercourse. The authors conclude that a transvaginal approach for specimen removal after laparoscopic resection of adnexal masses may offer the advantage of less postoperative pain than the classical umbilical retrieval.

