Table 1 (Appendix I) gives a cumulative overview of patient characteristics and relevant perioperative data. Individual patient data are presented in Table 2 (Appendix II). Mean operation time was 32 minutes (range 20 to 50 minutes). Five women had had previous pelvic surgery. There were no intraoperative complications and only one patient had a postoperative cystitis for which oral antibiotic therapy was administered. The mean drop in haemoglobin level was 0.9 g/dl (range 0 to 2.1 g/dl). Most women reported a low postoperative pain score (range 0 to 2) measured at day 1 following surgery by a visual analogue scale (VAS). The mean size of the removed adnexal mass was 51.8 mm (35-110 mm). Each patient was examined six weeks after surgery. There was no vaginal wound infection nor dehiscence, and no patient complained of pain during pelvic examination. All women were in good health and were all satisfied with the result.

Based on this observational case-series we concluded that adnexectomy by vNOTES is feasible for masses up to 110 mm even when performed with reusable, conventional laparoscopic instruments. The potential benefits with vNOTES are better cosmetics, low postoperative pain scores, and easy removal of the specimen without spillage. We stated that this new technique may enable surgeons in low resource settings to perform procedures by vNOTES since no expensive devices or instruments are needed.

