APPENDIX VI VAS scale

APPENDIX VII: Participant's pain log book

NOTABLE trial

First & last name:	
Date of surgical procedure:	

Arrival at home:

Time of arrival at home:

Pain score:

0	1	2	3	4	5	6	7	8	9	10

Pain medication:

	Dose in mg	Number of tablets	Time intake
Paracetamol			
Ibuprofen			
Other			

Day 1 after surgery:

Pain score morning:

0	1	2	3	4	5	6	7	8	9	10

Pain score evening:

0	1	2	3	4	5	6	7	8	9	10

Pain medication:

	Dose in mg	Number of tablets	Time intake
Paracetamol			
Ibuprofen			
Other			

Day 2 after surgery:

Pain score morning:

0	1	2	3	4	5	6	7	8	9	10

Pain score evening:

0	1	2	3	4	5	6	7	8	9	10

Pain medication:

	Dose in mg	Number of tablets	Time intake
Paracetamol			
Ibuprofen			
Other			

Day 3 after surgery:

Pain score morning:

0	1	2	3	4	5	6	7	8	9	10

Pain score evening:

0	1	2	3	4	5	6	7	8	9	10

Pain medication:

	Dose in mg	Number of tablets	Time intake
Paracetamol			
Ibuprofen			
Other			

Day 4 after surgery:

Pain score morning:

0	1	2	3	4	5	6	7	8	9	10

Pain score evening:

0	1	2	3	4	5	6	7	8	9	10

Pain medication:

	Dose in mg	Number of tablets	Time intake
Paracetamol			
Ibuprofen			
Other			

Day 5 after surgery:

Pain score morning:

0	1	2	3	4	5	6	7	8	9	10

Pain score evening:

0	1	2	3	4	5	6	7	8	9	10

Pain medication:

	Dose in mg	Number of tablets	Time intake
Paracetamol			
Ibuprofen			
Other			

Day 6 after surgery:

Pain score morning:

0	1	2	3	4	5	6	7	8	9	10

Pain score evening:

0	1	2	3	4	5	6	7	8	9	10

Pain medication:

	Dose in mg	Number of tablets	Time intake
Paracetamol			
Ibuprofen			
Other			

Day 7 after surgery:

Pain score morning:

0	1	2	3	4	5	6	7	8	9	10

Pain score evening:

0	1	2	3	4	5	6	7	8	9	10

Pain medication:

	Dose in mg	Number of tablets	Time intake
Paracetamol			
Ibuprofen			
Other			

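### The lower-number rule for the day 1–7 pain VAS turns all pain below 1 into zero, where the protocol's own day-1 figures lie, and the log book does not match the rule

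*Protocol*

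**What the plan says.** Section 5.3 defines postoperative pain as a score "measured using a VAS scale twice daily from day 1 till 7 self-reported by the participating women", one reading in the morning and one in the evening. The reading method is specific: "The participants should place the cursor of the VAS scale device available at the day care unit", then turn the device over and report the result as follows: "recording the numbers immediately to the left and right of the red line: e.g. pain level 0 to 1, or pain level 5 to 6". Of the two numbers, the lower goes into the analysis: "The lowest number will be recorded by the outcome assessor for data analysis".

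The participant's log book (Appendix VII) gives one row of boxes, 0 to 10, for each morning and each evening. It does not say whether to mark one box or two, or how to place a reading that falls between two numbers.

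Section 5.3 calls the score ordinal. Section 6.3 treats VAS scores as continuous and compares means by analysis of covariance and by multilevel models for repeated measurements, so the difference in means is the quantity to check. The protocol gives no expected difference, sample size or power for pain.

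**The concern.** Taking the lower number is rounding down. Well above zero it subtracts about half a point from both arms and cancels in the comparison. Near zero it does not cancel. A woman with no pain loses nothing, a woman at 0.9 loses 0.9, and both are entered as 0. The arm with more women at or close to zero loses less, so the difference between arms shrinks.

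The protocol's own evidence places early pain in that region. Section 1.4.3 says of the case series: "Most women reported a low postoperative pain score (range 0 to 2) measured at day 1 following surgery"; Appendix I adds a 24-hour mean of 1.3. The retrieval-route trial in section 1.4.1 reports "at 24 hours: 1.1 ± 1.5 vs 0.5 ± 1.4" for umbilical and vaginal retrieval.

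Less pain in the first postoperative week is a listed research question (section 1.6) and part of the rationale for vNOTES. The rule would bias the answer towards no difference. If only the lower number is captured, no later analysis can recover what was discarded, so this belongs in the protocol.

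The mismatch with the log book adds a comparability problem: the same pain could be scored differently depending on how and where it is written down.

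**Working it through.** **Inputs.** The rounding rule is from section 5.3. Means 1.1 and 0.5, with SDs 1.5 and 1.4, are the 24-hour values in section 1.4.1. The planned size of 66 (33 per arm) is from section 6.1. The shape of the pain distribution is not in the documents, so several shapes are assumed, all limited to 0–10. There is no pain calculation in the plan to reproduce.

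**Formulas.** True mean = ∫ P(X > x) dx from 0 to 10. Mean after taking the lower number = Σ P(X ≥ k), k = 1 to 10. Standardised difference = difference / √[(s₁² + s₂²)/2].

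**One case by hand.** For an exponential score with mean m, the mean after rounding down is 1/(e^(1/m) − 1), ignoring the cap at 10.
- m = 1.1: 1/(2.482 − 1) = 0.675
- m = 0.5: 1/(7.389 − 1) = 0.157
- Recorded difference: 0.675 − 0.157 = 0.518, against a true 0.60. Kept: 0.518/0.60 = 86%.
- Share below 1, hence recorded as 0: 1 − e^(−1/1.1) = 60% and 1 − e^(−2) = 86%.

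**All shapes with means 1.1 and 0.5.**

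| Assumed shape | SDs | Difference, true → recorded | Lost | Standardised, true → recorded | Lost |
|---|---|---|---|---|---|
| Normal, negatives set to 0 | 1.5 / 1.4 | 0.60 → 0.43 | 28% | 0.41 → 0.33 | 20% |
| Gamma | 1.5 / 1.4 | 0.61 → 0.40 | 34% | 0.44 → 0.31 | 30% |
| Exponential plus 40% / 70% exact zeros | about 1.4 (pooled) | 0.60 → 0.46 | 23% | 0.42 → 0.35 | 16% |
| Exponential | 1.1 / 0.5 | 0.60 → 0.52 | 14% | 0.70 → 0.64 | 9% |
| Gamma, SD 1.3 × mean | 1.43 / 0.65 | 0.60 → 0.53 | 12% | 0.54 → 0.51 | 6% |

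The first two rows match the cited SDs and the third comes close to them. The last two use smaller SDs as a sensitivity range.

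**Where the loss stops.**
- Gamma means 2.0 and 1.4 (SD 1.2): 0.60 → 0.565, 94% kept.
- Mid-scale means 4.0 and 3.4: 0.60 → 0.60, nothing lost.

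**Precision, for illustration.** For one comparison at 24 hours with 33 per arm (two-sided 5%), power in the first three rows falls from about 0.39–0.43 to 0.24–0.30. Repeated measures would change these values.

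**Alternative rules, same shapes.** The nearest whole number keeps 0.59–0.64. For the exponential case, the mean is e^(0.5/m)/(e^(1/m) − 1), which gives 1.063 − 0.425 = 0.638. The nearest 0.5 keeps 0.60–0.61.

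**The case against.** The strongest reply is that the effect is limited and its size rests on assumption. That stands in part. The distribution is not given, the loss ranges from 12% to 34% across the shapes tried, and it nearly vanishes once means reach about 1.4 to 2.0. The rule applies alike to both arms under blinding, works against the new technique rather than for it, and touches a secondary outcome in a pilot trial. None of this gives a reason to keep the rule.

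It can also be said that section 5.3 may itself be the instruction for filling in the log book, so that no two instruments run in parallel. The documents do not settle this. If so, the log book still lacks the instruction.

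A reader might infer more than the documents support:

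- **That the trial expects a difference of about half a point.** It states none. The 0.6 comes from a trial of retrieval route in which both arms had laparoscopic resection.
- **That starting on day 1 misses most of the effect.** In that trial the raw difference falls from 1.4 (1 hour) to 1.0 (3 hours) to 0.6 (24 hours). So 0.6/1.4 = 43% of the 1-hour difference remains, but 0.6/1.0 = 60% of the 3-hour difference. With the printed SDs the standardised differences are about 0.56, 0.50 and 0.41, a modest decline. Days 1 to 7 fit a question about the first postoperative week, and adding an earlier score would be a trade-off rather than a correction.
- **That every VAS reading is rounded down.** The rule is given only for the day 1–7 pain score. The recovery-room VAS (Appendix V) and the dyspareunia scales (Appendix VIII) carry no such rule.

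**Conclusion.** The point holds for the recording rule and its fit with the log book. Section 5.3 discards the 0-to-1 range, and the protocol's own early pain figures lie close to it. If day-1 means are near 1.1 and 0.5, a true difference of 0.60 would be recorded as roughly 0.40 to 0.53. Every low-pain shape tried moved in the same direction. The size depends on the assumed shape and on figures borrowed from a different comparison, so the range should be quoted rather than a single value. The primary outcome is unaffected. This is a minor to moderate point on a secondary outcome with no stated power, worth correcting because the correction is nearly free.

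**What to change.** In section 5.3, replace the lower-number rule by recording the cursor position to the nearest 0.5, or to the nearest whole number. Print the same reading rule in Appendix VII, so that scores taken in hospital and at home are comparable. The nearest whole number fits the existing boxes with one added line of instruction; the nearest 0.5 needs half-point boxes or a write-in space.

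Using the midpoint of each interval would not help. If a cursor at 0 is also read as 0 to 1, it adds the same half point to every score and restores none of the lost difference.

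The cost is a sentence in section 5.3, a small change to the log-book page, and a slightly finer reading by participants. No additional assessment is needed.

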Given its potential benefits, including no visible scars, fewer port-related complications, and less painful and faster post-operative recovery, we have introduced transvaginal pure NOTES (vNOTES) for the treatment of benign adnexal masses in our surgical practice since November 2013. A case-series by our group describing the technical feasibility of removing benign adnexal masses by vNOTES in 20 women has been published recently (7). Most women reported a low postoperative pain score (range 0 to 2) measured at day 1 following surgery by a visual analogue scale (VAS). Based on these preliminary observational findings we decided to design a pilot randomized trial to study the effectiveness of the new vNOTES approach based on the hypothesis that the new technique is at least as effective for removing a benign adnexal mass without cyst rupture compared to the classical laparoscopic technique.

Objective: To compare vNOTES and established laparoscopic removal of benign adnexal masses

Study design: Randomised controlled/single centre/single-blinded/parallel-group/non-inferiority/efficacy trial.

Study population: Women with symptomatic or persistent benign adnexal masses detected by clinical examination and ultrasound.

Randomisation: After assessment of eligibility/ informed consent women will be randomly allocated to undergo one of two techniques for removal of the benign adnexal mass before surgery by using a computer generated randomisation list. We will use stratified randomisation according to the cyst diameter.

Intervention: Women will be treated by a surgeon who is not blinded to the treatment allocation and who is equally skilled in performing both techniques. In the intervention group a vNOTES technique will be used.

Control: In the control group surgery will be done by a classical laparoscopic technique.

Participants, nursing staff and outcome assessors will be blinded by the use of mock surgical skin incisions. Pre- and postoperative treatment will be provided by staff blinded for the allocated intervention using a standardized protocol that is identical for both techniques. All women will be advised not to work during a 4-week period and to abstain from sexual intercourse until their 6-week booked appointment for a postoperative assessment.

Main study parameters/endpoints:

Primary outcomes: successful removal of a benign adnexal mass without spill.

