1.6. Objectives of the NOTABLE Trial

Is a vNOTES adnexectomy at least as effective compared to the standard transabdominal laparoscopic approach (LSC) for removing a benign adnexal mass without spill?

Secondary research questions are:

- Do more women treated by vNOTES prefer to leave the hospital on the day of surgery compared to LSC?
- Do women treated by vNOTES suffer from less pain compared to women treated by LSC in the first postoperative week?
- Is the removal of a benign adnexal mass by vNOTES faster compared to LSC?
- Does a vNOTES cause more pelvic infection or other complications compared to LSC?
- Does a vNOTES result in more hospital readmissions during the first six weeks following surgery compared to LSC?
- Does a vNOTES approach result in more women reporting dyspareunia, less quality of life or less sexual wellbeing at 3 or 6 months after surgery when compared to women treated by LSC?
- What are the costs of a vNOTES compared to LSC?

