4. TREATMENT ALLOCATIONS

4.1. Surgical procedures

The principal investigator, who has training and experience in both laparoscopy and NOTES, will perform all surgical procedures. He is therefore not blinded. All vNOTES participants will be blinded by three superficial “mock” skin incisions similar to those routinely done with the laparoscopic technique. The wound bandages will be left in place until the day 7 postoperative control to be removed by the coordinating investigator who will state at that moment that the wound healing has left an almost invisible scar as expected. This procedure aims to blind the participants, personnel and outcome assessors. The practice of performing “mock” incisions should not be considered as unethical: it is a procedure that has already been used in some surgical trials to minimise performance and detection bias whenever a subjective outcome is measured (22). The decision to use “mock” surgery is based on the clinical equipoise regarding the balance between benefits and adverse events for the two interventions under comparison (23).

4.1.1 vNOTES adnexectomy

This is the surgical procedure done in the intervention arm of the NOTABLE trial.

Clindamycin vaginal cream is administered on admission of the study participant to the outpatient ward.

The patient is placed in lithotomy position in a vacuum mattress. The abdomen, the vulva and the vagina are disinfected with an alcoholic betadine solution and draped. A Foley catheter is inserted into the bladder.

Three superficial skin incisions are made, one deep in the umbilicus and one in the left and right iliac fossa lateral of the epigastric vessels, and in the suprapubic region. The small vertical intraumbilical skin incision is closed with a monocryl 3/0 intradermal suture. Wound bandages are applied to all three skin incisions.

A 2.5 cm posterior colpotomy is made using a cold knife. The pouch of Douglas is opened using cold scissors. A Gelpoint Mini (Applied Medical) is used as vNOTES port and is inserted into the pouch of Douglas. CO₂ is insufflated until a maximal intraperitoneal pressure of 15mmHg. An optic is inserted and the peritoneal cavity is inspected. The patient is now placed in Trendelenburg position. The small intestine is lifted out of the pelvis.

The ureter is identified, but not routinely dissected. It is only dissected if it cannot be identified transperitoneally. The proximal end of the Fallopian tube is coagulated at its origin into the uterus

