4.1.2 LSC adnexectomy

This is the surgical procedure done in the control arm of the NOTABLE trial.

Clindamycin vaginal cream is administered on admission of the study participant to the outpatient ward.

The woman is placed in lithotomy position in a vacuum mattress. The abdomen, the vulva and the vagina are disinfected with an alcoholic betadine solution and draped. A Foley catheter is inserted into the bladder.

A small vertical intra-umbilical skin incision is made. A Verress needle is inserted into the peritoneal cavity; the correct position of the needle tip is checked with Semm test. CO₂ is insufflated until a maximal intraperitoneal pressure of 15mmHg. The Verress needle is removed and replaced by a 10mm reusable trocar. An optic is inserted through the 10mm trocar and the peritoneal cavity is inspected. The patient is now placed in Trendelenburg position. Two reusable 5mm trocars are placed under direct vision in the left and right iliac fossa lateral of the epigastric vessels. The small intestine is lifted out of the pelvis.

The ureter is identified, but not routinely dissected. It is only dissected if it cannot be identified transperitoneally. The proximal end of the Fallopian tube is coagulated at its origin into the uterus using a reusable bipolar grasper and cut using cold scissors. The ovarian ligament is coagulated and cut. The infundibulopelvic ligament is coagulated and cut. The adnexa are resected and placed in an endobag (Memobag, Teleflex). If necessary, the same procedure is repeated for the contralateral side.

The peritoneal cavity is rinsed and haemostasis is checked. No drains are left in the peritoneal cavity except when there might be any uncertainty concerning the haemostasis. The 5 mm trocars are removed under direct vision. The purse string of the endobag is pulled through the 10 mm trocar upon removal of the optic. The umbilical incision is extended vertically in caudal direction, the size being not more than 2.5 cm. The fascia and peritoneum are opened and the proximal end of the endobag is pulled through the incision without causing any rupture if possible. If not possible, the endobag should be opened and the content of the cyst should be aspirated to reduce the volume of the adnexa. The aspirated fluid should be send for cytological examination. The endobag is now removed with the adnexa inside it.

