APPENDIX III

CLAVIEN-DINDO CLASSIFICATION

[figure not shown]
TABLE 1. Classification of Surgical Complications

Grade	Definition
Grade I	Any deviation from the normal postoperative course without the need for pharmacological treatment or surgical, endoscopic, and radiological interventions Allowed therapeutic regimens are: drugs as antiemetics, antipyretics, analgetics, diuretics, electrolytes, and physiotherapy. This grade also includes wound infections opened at the bedside
Grade II	Requiring pharmacological treatment with drugs other than such allowed for grade I complications Blood transfusions and total parenteral nutrition are also included
Grade III	Requiring surgical, endoscopic or radiological intervention
Grade IIIa	Intervention not under general anesthesia
Grade IIIb	Intervention under general anesthesia
Grade IV	Life-threatening complication (including CNS complications)* requiring IC/ICU management
Grade IVa	Single organ dysfunction (including dialysis)
Grade IVb	Multiorgan dysfunction
Grade V	Death of a patient
Suffix "d"	If the patient suffers from a complication at the time of discharge (see examples in Table 2), the suffix "d" (for "disability") is added to the respective grade of complication. This label indicates the need for a follow-up to fully evaluate the complication.

*Brain hemorrhage, ischemic stroke, subarachnoidal bleeding, but excluding transient ischemic attacks.
CNS, central nervous system; IC, intermediate care; ICU, intensive care unit.

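### The any-grade complication outcome, and readmission, count events at the blinding-only mock skin incisions against vNOTES, which biases the safety comparison against vNOTES and dilutes any benefit of avoiding ports.

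*Protocol*

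**What the plan says.** Protocol Section 5.3 lists among the secondary outcomes "Per- or postoperative complications according to the Clavien- Dindo classification detected during the first six weeks of surgery, as a dichotomous outcome". Hospital readmission over the same six weeks is a separate yes/no outcome. Appendix III reproduces the grading scale. Its lowest grade covers any departure from a normal postoperative course, and "This grade also includes wound infections opened at the bedside".

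Section 4.1 states: "All vNOTES participants will be blinded by three superficial “mock” skin incisions similar to those routinely done with the laparoscopic technique". Section 4.1.1 then writes them into the vNOTES operation: "Three superficial skin incisions are made, one deep in the umbilicus and one in the left and right iliac fossa lateral of the epigastric vessels". Section 4.1 gives blinding as their only purpose.

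The safety question in Section 1.6 is "Does a vNOTES cause more pelvic infection or other complications compared to LSC". A further question there concerns readmissions. The Summary names "fewer port-related complications" among the potential benefits of vNOTES. Section 6.3 analyses by intention to treat first. Neither 5.3 nor 6.3 distinguishes complications or readmissions by site or cause.

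**The concern.** The mock wounds would not exist if vNOTES were used in practice; they belong to the trial's blinding. A haematoma, wound infection or dehiscence at one of them is nevertheless a Clavien-Dindo event in the vNOTES arm and turns that woman's outcome into a yes. A readmission for it does the same for the readmission outcome. Laparoscopy has no matching artificial wound, because its skin incisions are part of the technique.

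The result would be read as an answer about vNOTES, but it describes vNOTES with sham incisions added. With 33 women per arm, readers will look at raw counts, and one or two wound events can change the impression given. If site is not collected prospectively, separating these events later means attributing them from narratives after the fact, possibly with knowledge of the arm.

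**Working it through.** **Inputs**
- Women per arm: 33, from the 66 planned in Section 6.1 with equal allocation. The plan's sample-size figures reproduce at a one-sided 5% level: (1.645 + 0.842)² × 2 × 0.95 × 0.05 / 0.15² = 26.1, so 27 per group and 54 in total; 54 / 0.85 = 63.5, so 64. These concern the primary outcome. The protocol states no planning figure for complications.
- Mock-wound complication rate m: not in the protocol. Assumed 1%, 3% and 5%.
- Rate c of other complications, taken as equal in both arms, and laparoscopic access-wound rate w: not in the protocol. Assumed for illustration only.

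**Step 1. Does a mock-wound event count?** The outcome takes any grade, the lowest grade admits wound events, the mock incisions are a written step of one arm only, and no exclusion is stated. It counts. This follows from the absence of a rule; the protocol does not say it outright.

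**Step 2. How many events?** Expected number = 33 × m; chance of at least one = 1 − (1 − m)^33.

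| m (assumed) | Expected events | Chance of at least one |
|---|---|---|
| 1% | 0.33 | 28% |
| 3% | 0.99 | 63% |
| 5% | 1.65 | 82% |

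**Step 3. Effect on the comparison.** With independent sources, the laparoscopy rate is 1 − (1 − c)(1 − w) and the vNOTES rate is 1 − (1 − c)(1 − m). Counting mock wounds raises the vNOTES rate by (1 − c) × m, whatever w is.

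Take c = 5% and w = 10%. Laparoscopy is 1 − 0.95 × 0.90 = 14.5%.

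| Mock-wound events | vNOTES rate | Difference in favour of vNOTES | Power, 33 per arm, two-sided 5% |
|---|---|---|---|
| Left out | 5.0% | 9.5 points | about 25% |
| Counted, m = 3% | 7.85% | 6.65 points | about 13% |
| Counted, m = 5% | 9.75% | 4.75 points | about 9% |
| Counted, m = 10% (= w) | 14.5% | 0 points | – |

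The difference vanishes only if superficial mock wounds cause as many complications as real access wounds. With w from 5% to 15% and c from 5% to 10%, power with mock events left out is still only about 8% to 42%.

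**Step 4. Are mock and port wounds equivalent?** No. In Section 4.1.2 only laparoscopy has planned entry through the abdominal wall ("A Verress needle is inserted into the peritoneal cavity"), followed by one 10 mm and two 5 mm trocars, an umbilical incision of up to 2.5 cm and an opened fascia. Visceral, vascular, fascial and deep port-site events can by plan arise only in that arm, and they still count.

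**Step 5. Does the infection outcome share the problem?** Hardly. Section 5.3 requires lower abdominal pain with fever above 38 °C plus positive signs or laboratory findings. A superficial infection of a mock wound is unlikely to meet that alone.

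**The case against.** The strongest reply is that this is a secondary outcome of a pilot. The primary outcome is settled at the end of surgery and is untouched. For a question about excess harm, counting mock wounds errs on the cautious side, against the new technique. Power is too low for a decision to turn on the rule. Section 9.6 has all adverse events recorded, and supplementary tabulations are usually left to the SAP, which is not at hand. Much of this stands, and it limits the weight of the point. It does not remove it: the protocol itself fixes the outcome as one undifferentiated yes/no, the resulting bias has a known direction, and Section 9.6 does not require the site that a later analysis would need.

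Two stronger readings are tempting and unsupported.
- A reader might infer that the trial cannot show fewer port-related complications. Step 4 shows that the contrast is diluted, not abolished. Fewer port-related complications is also background rationale, not an objective or an endpoint.
- A reader might set the assumed mock-wound events beside the complication rate below 1% in Section 9.8 (under 33 × 1% = 0.33 events) and conclude that they outnumber all genuine events. Section 9.8 does not say that its figure covers every grade, and one of its two cited sources is by title a study of major complications. In the protocol's own series (Section 1.4.3), one of 20 women had a cystitis treated with antibiotics, which is Grade II in Appendix III. That is 5%, or 33 × 5% = 1.65 events, although it rests on a single case. It equals the top of the assumed mock-wound range, so the inference fails.

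**Conclusion.** The point holds in a limited form. As written, the complication outcome, and readmission for the same cause, charges vNOTES with events at wounds made only for blinding. The comparison estimates vNOTES plus sham incisions versus laparoscopy, and so biases the answer to the Section 1.6 question against vNOTES.

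The size cannot be taken from the protocol. Under assumed mock-wound rates of 1%, 3% and 5%, about 0.3, 1.0 and 1.7 extra events are expected in 33 women. In the illustration, a 5% rate halves a 9.5-point advantage to 4.75 points. All of these rest on assumed rates, equal allocation and complete six-week follow-up. An advantage from avoiding ports could still appear, though with low power whether or not mock events are counted.

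**What to change.** - On the complication and readmission forms, record the site of each event or cause: abdominal skin wound, vaginal wound, internal, or general. The blinded assessor codes this without reference to arm, since abdominal skin wound is a valid category in both.
- Keep the all-event intention-to-treat comparison as the main one, so that no harm is hidden.
- In Section 6.3, prespecify a supplementary comparison for complications and readmission. In the vNOTES arm it leaves out events confined to mock skin incisions, except where a mock site served as a real port after conversion. In the laparoscopy arm it keeps port-wound events. The statistician applies the rule from the allocation and the operative record.
- Leave the infection outcome as it is.
- Reconcile the description of the mock sites in Section 4.1.1, which announces three incisions but names the umbilicus, both iliac fossae and the suprapubic region, so that the site coding has a fixed list.

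Cost: one extra form field, a short addition to Section 6.3 and one more tabulation, which will itself have low power.
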